3.1 Primary

[figure not shown]
The primary objective is to document the safety of pasireotide s.c. in patients with Cushing's disease.

3.2 Secondary

The secondary objectives are:

- To document the efficacy of pasireotide s.c. in normalizing mean 24h-UFC at Week 12, 24 and 48, separately,
- To document the efficacy of pasireotide s.c. in achieving at least 50% reduction of mean 24h-UFC from baseline at Week 12, 24 and 48, separately,

- To document the changes in clinical signs and symptoms,
- To document the changes in patient-reported outcome questionnaires (CushingQoL and WPAI-GH),
- To document the effects of pasireotide s.c. on the GH/IGF-1 axis.
- To document the overall safety and tolerability of pasireotide s.c. in patients with CD

4 Definitions and general methodology

4.1 Study drug start and end date

Study drug start date is defined as the first date when a non-zero dose of study drug was administered and recorded on the Drug Administration Record (DAR) CRF page.

Similarly, **study drug end date** is defined as the last date when a non-zero dose of study drug was administered and recorded on the DAR CRF page of the study.

4.2 Study day

Study day is defined to be the number of calendar date from study drug start to any event date.

For events that occurred on or after study drug start date (e.g. lab samples, AEs), study day is computed using following formula:

- $Study\ day = (event\ date - study\ drug\ start\ date) + 1\ day$

For events prior to study drug start date (e.g. time of diagnosis), study day is computed using following formula:

- $Study\ day = (event\ date - study\ drug\ start\ date)$

Note that study drug start date is study day 1 and the day before study drug start date is study day -1, therefore there is no study day 0. Unless stated otherwise, one month is defined as a 28 days period.

4.3 Baseline definition

For efficacy and safety evaluations, *baseline assessment* is defined as the last available value (or assessment) prior to study drug start date. If for a given parameter, a patient had no value

(or assessment) prior to study drug start date, baseline will be considered missing for that efficacy and/or safety evaluation.

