To document the changes in patient-reported outcome questionnaires (CushingQoL and WPAI-GH)	The change from baseline to Week 12, 24 and 48 in CushingQoL and WPAI-GH scores	
To document the effects of pasireotide s.c. on the GH/IGF-I axis	The change from baseline to Week 12, 24 and 48 in GH and IGF-I separately	
To document the overall safety and tolerability of pasireotide s.c. in patients with CD	Incidence of AEs, and laboratory, vital signs and electrocardiographic abnormalities. Changes in laboratory values, electrocardiograms readings, and in vital signs values.	

4 Study design

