4.1 Description of study design

This is an open-label, uncontrolled, single-arm, multi-center, multi-national expanded access study. The starting dose will be:

- [Applicable for countries in the European Union] 600 µg b.i.d. (twice daily) in all patients also including the ones with impaired glucose metabolism with the option to increase the dose to 900 µg b.i.d. if the patient is not controlled (i.e. 24h-mean UFC levels above the upper limit of normal) at earliest after 2 months of treatment provided the 600 µg b.i.d dose is well tolerated by the patient. However ongoing patients in the study at the time of approval of amendment 3 will continue on their current dose.
- [Applicable for countries outside the European Union] 900 µg b.i.d. (twice daily). The initial dose for patients with impaired glucose metabolism will be 600 µg b.i.d

Refer to [Section 6.2.1](#) for allowed dose modifications.

After a 21-day screening period, patients who satisfy all the inclusion/exclusion criteria will start receiving pasireotide s.c. twice a day. Please, refer to [Table 7-1](#) for a description of the screening evaluations required. During the first 24-week period, patients will have a visit on a weekly basis up to week 4 and will then be followed on a 4-week basis up to week 24. In the second study period, patients will be followed at 12-week intervals until the end of the study. Patients will be treated until the drug is approved for commercial use and reimbursed in each respective country or until 31 December 2015 (until 31 December 2016 for sites in South Korea and Brazil), whichever occurs first.

[figure not shown]

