6.3 Concomitant medications

All medications, including over the counter medications (OTC), taken prior to the first study drug administration and which continue after visit 2 (beginning of the treatment) are to be recorded on the Concomitant Medication section of the CRF.

However, investigators should discourage patients from taking any medication during the study, with the exception of medications that are required to treat an adverse event.

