HbA _{1c}	D	7.2.2.4.3.	X				X		X			X	X	X	X	X	X	X	
Vitamin B12	D	7.2.2.4.3.	X					X			X		X					X	
Urinary free cortisol and urine creatinine	D	7.2.1.1.1.	X					X	X	X	X	X	X	X	X	X	X	X	
Serum cortisol	D	7.2.1.1.2.	X			X		X	X	X	X	X	X	X	X	X	X	X	
Plasma ACTH	D	7.2.1.1.2.	X		X		X	X	X	X	X	X	X	X	X	X	X	X	
HbsAg and anti-HCV	D	7.2.2.4.6.	X																
Signs and symptoms of Cushing's disease	D	7.2.1.1.3.	X	X	X	X	X	X	X	X	X	X	X	X	X	X	X	X	
Cushing's syndrome HRQoL and WPAI-GH questionnaire	D	7.2.1.1.4 7.2.1.1.5.		X				X		X			X	X	X	X	X	X	
Urinalysis	D	7.2.2.4.4.	X						X			X		X	X	X ^b	X	X	
Serum Pregnancy test	D	7.2.2.4.5.	X							X					X	X	X	X	
ECG	D	7.2.2.5.1.	X	X	X	X	X	X	X	X	X	X	X	X	X	X	X	X	
Adverse events	D	8.1.													Continuously				
Prior/Concomitant medications	D	6.3.	X												Continuously				
Drug administration	D	6.1.													Continuously				
Study phase completion record	D	7.1.3.															X		
Study completion record	D	7.1.4.																X	

	Category	Reference to Section	Screening	Baseline	Study period													Study Phase Completion	Study Completion
					1	2	3	4	5	6	7	8	9	10	11	12	13, 14,... ^a		
Visit Number																		776	777
Study Week		7.1.2.	-3 to 0	0	1	2	3	4	8	12	16	20	24	36			48, 60,... ^a	Last dose	Last dose + 4
Study days		7.1.2.	-21 to -1	0	7	14	21	28	56	84	112	140	168	252	336, 420, ^a			Last dose	Last dose + 28

^a One visit every 12 weeks/84 days until patients are transitioned to commercial pasireotide or until 31 December 2015 (until 31 December 2016 for sites in South Korea and Brazil), whichever comes first

^b To be done every 24 weeks after visit 13

D Data/assessments to be entered in the database

S Data/assessments that remain in source documents only, not to be recorded on CRF

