4.4 Visit windows

It is anticipated that some assessments could be done outside the protocol planned visit windows, for that purpose a computed Visit windows schedule is defined.

Visits after the date of first dose are scheduled weekly for the first 4 weeks and then monthly from study day 28 (visit number 6) to study day 168 (visit number 11). Thereafter every 12 weeks/84 days.

Table 4-1 Visit windows

Study visit	Week	Visit window	Visit window Start*	Visit window Mid-point*	Visit window End*	Visit window Duration
1 (Screening)	-1	-1	-21	0	-1	21
2 (Baseline)	0	0	0	0	0	1
3	1	1	1	7	11	7
4	2	2	12	14	18	7
5	3	3	19	21	25	7
6	4	4	26	28	32	7
7	8	5	33	56	70	28
8	12	6	71	84	98	28
9	16	7	99	112	126	28
10	20	8	127	140	154	28
11	24	9	155	168	182	28
12	36	10	183	252	294	84
13	48	11	295	336	378	84
14	60	12	379	420	462	84
15	72	13	463	504	546	84
16	84	14	547	588	630	84
17	96	15	631	672	714	84
18	108	16	715	756	798	84
19	120	17	799	840	882	84
20	132	18	883	924	966	84
21	144	19	967	1008	1050	84
22	156	20	1051	1092	1134	84

*Note: * study day*

For summary statistics (tables) for all laboratory data assessment visits are processed as follows:

1. Unscheduled visits are used.

2. Unless stated otherwise, the closest assessment to the mid-point of each visit-window is considered.
3. In case 2 or more assessments are reported on the same day, or have the same distance from the mid-point, i.e. 2 days before, 2 days after, then the mean will be taken.

With regard to mean 24h-UFC, the above rules do not apply as per protocol there are particular definitions, see section 5.2.1 for further details.

All lab assessments are listed.

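### SAP 4.3 excludes assessments made on the first-dose date, so a patient first dosed on the Visit 2 date has no CushingQoL or WPAI-GH baseline

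*SAP*

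**What the plan says.** SAP 4.3 states that baseline, for efficacy and safety alike, "is defined as the last available value (or assessment) prior to study drug start date". Where a patient has no such value, "baseline will be considered missing for that efficacy and/or safety evaluation". The reference point comes from SAP 4.1: "Study drug start date is defined as the first date when a non-zero dose of study drug was administered". It is a calendar date and carries no time of day.

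Protocol Table 3-1 lists as a secondary endpoint "The change from baseline to Week 12, 24 and 48 in CushingQoL and WPAI-GH scores". In protocol Table 7-1, the row labelled "HRQoL and WPAI-GH questionnaire" is blank under Screening and has its first mark under Baseline, which is Visit 2.

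On when dosing starts, protocol 4.1 says: "After a 21-day screening period, patients who satisfy all the inclusion/exclusion criteria will start receiving pasireotide s.c. twice a day". Protocol 6.3 is more specific. It refers to medications "which continue after visit 2 (beginning of the treatment"), which identifies Visit 2 with the start of treatment. SAP 4.4 adds: "Visits after the date of first dose are scheduled weekly for the first 4 weeks".

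**The concern.** The SAP rule and the visit schedule do not fit together. If the first injection is given on the Visit 2 date, the questionnaires completed at that visit share their date with drug start and fail the SAP 4.3 test. No earlier questionnaire is planned, so baseline is missing and the change score does not exist.

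Two smaller consequences follow from the same rule:

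- **Clinical signs.** These are assessed at both Screening and Visit 2, so baseline falls back to the screening value. Protocol 10.5.1 lets a screening value serve as baseline for parameters not assessed at the baseline visit. By implication, the Visit 2 value is meant where one is scheduled. That section covers efficacy variables and sets no such rule for safety parameters.
- **Worst-value summaries.** SAP 5.3.1 starts the on-treatment period on the day of first dose. A pre-dose Visit 2 value on that date can therefore be picked up as a worst on-treatment laboratory value (liver tests, PT/INR) under SAP 5.3.3, or as a worst post-baseline vital sign under SAP 5.3.4. It alters a result only if it is that patient's most extreme value.

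**Working it through.** The plan gives no figure on this point to reproduce, so the check applies its rules to dates.

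**1. Does a same-day assessment qualify?** SAP 4.2 gives study day = (event date − start date) + 1 for events on or after drug start, and (event date − start date) for earlier events. SAP 4.3 requires event date < start date.

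| First dose | Study day of the Visit 2 record | Before start date? | Questionnaire baseline |
|---|---|---|---|
| On the Visit 2 date | 0 + 1 = 1 | No | Missing |
| 1 day after Visit 2 | −1 | Yes | Visit 2 value |
| 2 days after Visit 2 | −2 | Yes | Visit 2 value |

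SAP 4.2 separates events on or after the start date from events before it. The cut-off therefore cannot be read loosely as meaning before the first injection.

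**2. Is there an earlier questionnaire?** The extracted Table 7-1 row has 16 cells for 15 visit columns (Screening, Baseline, Visits 3 to 12, Visit 13 onward, 776, 777), so its alignment needs checking. Read from the left, the cells are: blank, X, three blanks, X, blank, X, two blanks, six X. Cells 2, 6, 8, 11, 12 and 13 are Baseline and Weeks 4, 12, 24, 36 and 48, which include all three endpoint weeks. Moved one column left, the marks miss Week 12. Moved one column right, they miss Weeks 12 and 24. Only the reading with Screening blank and Baseline marked fits the endpoint.

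**3. Does another rule supply a baseline?** SAP 4.9 defers to a parameter-specific definition, but the SAP gives one only for UFC (5.2.1). The CushingQoL and WPAI-GH paragraphs have none. SAP section 5 rules out imputation unless noted, and none is noted for the questionnaires.

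**4. How many patients?** The share dosed on the Visit 2 date is not documented. With the planned 200 patients, the most that can keep a questionnaire baseline is 200 × (1 − share):

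| Assumed same-day share | 0% | 25% | 50% | 75% | 100% |
|---|---|---|---|---|---|
| Patients with a baseline | 200 | 150 | 100 | 50 | 0 |

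The schedule points towards the right of this table. Screening runs from day −21 to −1, Baseline is day 0, Visit 3 is day 7, and the SAP counts the weekly visits from the first dose. That is a plan, not a count.

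**5. Clinical signs.** With screening on days −21 to −1 and Visit 2 on day 0, the fallback value is 1 to 21 days older than the Visit 2 value.

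**6. By-visit Week 1 laboratory tables.** The Week 1 window is days 1 to 11 with mid-point 7, and the closest value is used. A Visit 2 value on day 1 is 7 − 1 = 6 days away. Visit 3 within its ±2-day tolerance falls on study days 6 to 10, which is 0 to 3 days away. Any value on days 2 to 11 is at most 5 days away. The Visit 2 value is chosen only if the window holds nothing later, so these tables are normally unaffected.

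**The case against.** The strongest reply is that no passage states outright that the first dose is given on the Visit 2 date. Protocol 6.3 says so only in a parenthesis within a concomitant-medication rule, and patients inject themselves, so a later first dose is possible. SAP Table 4-1 puts Visit 2 on day 0 and opens the Visit 3 window on day 1, the drug start date under SAP 4.2. On that calendar, Visit 2 precedes drug start and would qualify. Together with the Visit 2 label in that table, this suggests that the authors meant Visit 2 to be baseline.

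This shows intent but does not cure the rule. SAP 4.2 says that day 0 does not exist, and no date produces it. A programmer who follows SAP 4.3 excludes the same-day record; one who follows the visit label departs from the written definition. The uncertainty about same-day dosing does stand, and for that reason the size is given only as a range.

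The extracted Table 7-1 is also imperfect. The HbA1c row has 16 cells too, and read from the left it gives Screening and Weeks 3, 8 and 20, which looks misaligned. The questionnaire row should therefore be confirmed against the PDF, although its fit to Weeks 12, 24 and 48 makes the reading used here much the more plausible.

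Finally, all analyses are descriptive, post-baseline questionnaire scores can still be summarised, and an empty change table would be noticed. These points limit the harm but do not remove the need to correct the text.

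**Conclusion.** The concern holds. As written, SAP 4.3 leaves any patient first dosed on the Visit 2 date without a CushingQoL or WPAI-GH baseline, and the stated change-from-baseline endpoint cannot be computed for that patient. Between 0 and about 200 patients are affected, depending on an undocumented share; the schedule makes same-day dosing the expected case.

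The conclusion assumes that the questionnaire row is blank at Screening and that no unscheduled questionnaire was completed before Visit 2. None is planned.

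The AE-based primary variable, UFC, GH and IGF-I are not affected. The effects on clinical signs and worst-value safety summaries are secondary, and their frequency is unknown. The SAP should be corrected, but the main safety conclusion does not depend on this point.

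The day 0 in Table 4-1, which is also given as the Screening mid-point, is a separate and minor labelling error. It does not cause the questionnaire loss.

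**What to change.** - **SAP 4.3.** Define baseline as the last non-missing pre-dose assessment on or before the study drug start date. State that Visit 2 questionnaires, clinical signs other than blood pressure, and scheduled Visit 2 laboratory values dated on the first-dose date count as baseline.
- **Timing guard.** Accept same-day heart rate, blood pressure and ECG as baseline only where records show that they preceded the first dose; otherwise keep the last earlier value. Protocol 1.2.2 reports a heart-rate reduction at 0 to 4 hours and a peak QTcF effect at 2 hours after dosing, in healthy volunteers at 1950 µg b.i.d. Protocol 7.2.2.2 and 7.2.2.5.1 set no timing relative to dose. The text should also say which rule covers body temperature.
- **SAP 5.3.** Exclude any record used as baseline from the worst on-treatment and worst post-baseline derivations.
- **SAP Table 4-1 (minor).** Map Visit 2 by its visit label, remove day 0, and align the table with the SAP 4.2 numbering.

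With this change, every patient with a completed pre-dose Visit 2 questionnaire has a baseline, whatever the share dosed that day. The cost is SAP wording and a small derivation change, with no new data for questionnaires, clinical signs or laboratory values. Two limits remain. Where no time was recorded, some heart-rate, blood-pressure and ECG baselines will still be screening values. Same-day laboratory values are taken as pre-dose without a clock time to prove it.

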4.4 Visit windows

It is anticipated that some assessments could be done outside the protocol planned visit windows, for that purpose a computed Visit windows schedule is defined.

Visits after the date of first dose are scheduled weekly for the first 4 weeks and then monthly from study day 28 (visit number 6) to study day 168 (visit number 11). Thereafter every 12 weeks/84 days.

Table 4-1 Visit windows

Study visit	Week	Visit window	Visit window Start*	Visit window Mid-point*	Visit window End*	Visit window Duration
1 (Screening)	-1	-1	-21	0	-1	21
2 (Baseline)	0	0	0	0	0	1
3	1	1	1	7	11	7
4	2	2	12	14	18	7
5	3	3	19	21	25	7
6	4	4	26	28	32	7
7	8	5	33	56	70	28
8	12	6	71	84	98	28
9	16	7	99	112	126	28
10	20	8	127	140	154	28
11	24	9	155	168	182	28
12	36	10	183	252	294	84
13	48	11	295	336	378	84
14	60	12	379	420	462	84
15	72	13	463	504	546	84
16	84	14	547	588	630	84
17	96	15	631	672	714	84
18	108	16	715	756	798	84
19	120	17	799	840	882	84
20	132	18	883	924	966	84
21	144	19	967	1008	1050	84
22	156	20	1051	1092	1134	84

*Note: * study day*

For summary statistics (tables) for all laboratory data assessment visits are processed as follows:

1. Unscheduled visits are used.

2. Unless stated otherwise, the closest assessment to the mid-point of each visit-window is considered.
3. In case 2 or more assessments are reported on the same day, or have the same distance from the mid-point, i.e. 2 days before, 2 days after, then the mean will be taken.

With regard to mean 24h-UFC, the above rules do not apply as per protocol there are particular definitions, see section 5.2.1 for further details.

All lab assessments are listed.

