. For example, if a patient answers all 12 items with 'Sometimes' or 'Somewhat', X = 36 and $Y = 100 \cdot 24/48 = 50$.

Similar analyses as defined above will also be performed at all other scheduled post-baseline assessments.

Changes from baseline to Week 12 , 24 and 48 in WPAI-GH scores

The WPAI-GH questionnaire is to assess work productivity and activity impairment.

WPAI outcomes are expressed as impairment percentages, with higher numbers indicating greater impairment and less productivity, i.e., worse outcomes, as follows (see [Reilly 2002](#)):

Questions:

- 1 = currently employed
- 2 = hours missed due to health problems
- 3 = hours missed other reasons
- 4 = hours actually worked
- 5 = degree health affected productivity while working
- 6 = degree health affected regular activities

Scores (multiply scores by 100 to express in percentages):

Percent work time missed due to health: $Q2/(Q2+Q4)$

Percent impairment while working due to health: $Q5/10$

Percent overall work impairment due to health:

$Q2/(Q2 + Q4)+[(1 - Q2/(Q2 + Q4)) \cdot (Q5/10)]$

[figure not shown]
Percent activity impairment due to health: $Q6/10$

Descriptive summaries of actual and percentage change in mean scores from baseline to Week 12, 24 and 48 will be provided. Similar analyses will also be performed at all other scheduled post-baseline assessments.

Changes from baseline in GH and IGF-I to Week 12, 24 and 48

Descriptive summaries of the absolute and relative change from baseline of GH and IGF-I at Week 12, 24 and 48 will be provided.

Similar analyses will also be performed at all other scheduled post-baseline assessments.

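### SAP Table 4-1: three stated window lengths do not match their own start and end days, and two boundaries assign late Week 4 and Week 24 laboratory samples to Week 8 and Week 36

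*SAP*

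**What the plan says.** SAP 4.4 defines computed visit windows for assessments made outside the protocol's planned windows. Table 4-1 gives each visit a start, mid-point, end and duration, labelled as study days. The Week 24 row reads "11 24 9 155 168 182 28" (visit, week, window number, start, mid-point, end, duration) and the Week 36 row reads "12 36 10 183 252 294 84".

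The scope of the rules is laboratory tables: "For summary statistics (tables) for all laboratory data assessment visits are processed as follows". The first rule is "Unscheduled visits are used". The second is "Unless stated otherwise, the closest assessment to the mid-point of each visit-window is considered". Samples tied on distance are averaged. One variable is exempt: "With regard to mean 24h-UFC, the above rules do not apply as per protocol there are particular definitions".

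SAP 4.2 makes the first-dose date study day 1 and adds "therefore there is no study day 0". SAP 5.2.1 names a by-visit laboratory output: "Descriptive summaries of the absolute and relative change from baseline of GH and IGF-I at Week 12, 24 and 48 will be provided". It promises similar analyses at the other scheduled visits.

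**The concern.** The table contradicts itself in three rows, so a programmer who uses start and end days and one who uses the stated durations would build different windows.

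The boundaries matter more. Visits go from weekly to 4-weekly after Week 4, and from 4-weekly to 12-weekly after Week 24. At both changes the earlier window keeps its short upper arm and the later window takes the rest of the gap. A Week 24 sample taken about two weeks late then cannot count as Week 24. If nothing closer to day 252 exists, it becomes the patient's Week 36 value. Patients who stop soon after Week 24 are the obvious source of such samples, because protocol 7.1.3 requires a completion evaluation on the day of the last dose. The Week 36 row could therefore mix values from about Week 26 to Week 30, from patients no longer on treatment at Week 36, with true Week 36 values.

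**Working it through.** **Inputs.** Start, mid-point, end and stated duration come from SAP Table 4-1. Protocol 7.1.2 allows ±2 days for visits 3 to 11 and ±5 days from visit 12.

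**Step 1: reproduce the durations.** Length = end − start + 1. This gives the stated figure in 19 of the 22 rows. The alternative, end − start, gives it in none. Selected rows:

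| Row | Start | Mid-point | End | Stated | End − start + 1 |
|---|---|---|---|---|---|
| Week 1 | 1 | 7 | 11 | 7 | **11** |
| Week 4 | 26 | 28 | 32 | 7 | 7 |
| Week 8 | 33 | 56 | 70 | 28 | **38** |
| Week 12 | 71 | 84 | 98 | 28 | 28 |
| Week 24 | 155 | 168 | 182 | 28 | 28 |
| Week 36 | 183 | 252 | 294 | 84 | **112** |
| Week 48 | 295 | 336 | 378 | 84 | 84 |

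**Step 2: compare boundaries with the halfway point between mid-points.**

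- Week 12/16: (84 + 112)/2 = 98; the table splits at 98/99.
- Week 36/48: (252 + 336)/2 = 294; the table splits at 294/295.
- Week 4/8: (28 + 56)/2 = 42; the table splits at 32/33, which is 42 − 32 = 10 days early.
- Week 24/36: (168 + 252)/2 = 210; the table splits at 182/183, which is 210 − 182 = 28 days early.

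These shortfalls equal the excess lengths of the later rows: 38 − 28 = 10 and 112 − 84 = 28. Keeping the stated durations and ends gives starts of 70 − 28 + 1 = 43 and 294 − 84 + 1 = 211.

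**Step 3: count the days placed in the farther visit.**

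| Mid-points used | Nearer Week 4, placed in Week 8 | Nearer Week 24, placed in Week 36 |
|---|---|---|
| As printed (28, 56, 168, 252) | days 33-41 (9 days; day 42 ties) | days 183-209 (27 days; day 210 ties) |
| In SAP study days (29, 57, 169, 253) | days 33-42 (10 days; day 43 ties) | days 183-210 (28 days; day 211 ties) |

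With printed mid-points, day 183 is 183 − 168 = 15 days from Week 24 and 252 − 183 = 69 days from Week 36. A completion sample on day 195 is 27 days from Week 24 and 57 from Week 36.

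**Step 4: can on-schedule visits fall there?** No. By the printed mid-points, the protocol windows are days 26-30 (Week 4), 54-58 (Week 8), 166-170 (Week 24) and 247-257 (Week 36). Only late, unscheduled or discontinuation samples reach days 33-41 or 183-209.

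**Step 5: day count.** The printed mid-points take baseline as day 0, which SAP 4.2 excludes. With those mid-points, days 11, 18 and 25 are each one day nearer the next weekly visit. In SAP study days this disappears: windows 12-18, 19-25 and 26-32 centre exactly on 15, 22 and 29.

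**The case against.** The strongest reply is that the stated durations do no work. Allocation uses start, end and mid-point only, so correcting the column to 11, 38 and 112 would change no output. That stands. A reader might infer that the wrong durations cause the mislabelling. They do not: boundary placement does, and it is a separate point. The Week 1 row has a wrong duration but causes no comparable misplacement.

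The reach is also narrow. A reader might infer that laboratory reporting generally is distorted. The summaries in SAP 5.3.3 are shift tables to the worst value, or for glucose-related parameters also the last value, plus listings. None depends on a visit label. Mean UFC is exempt. GH and IGF-I are the clearly specified by-visit laboratory changes, with named time points at Weeks 12, 24 and 48, and the Week 12 and 48 windows are sound. Everything is descriptive, with no hypothesis test, and all laboratory values are listed.

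The trigger is narrow too. A Week 24 value is lost only if no sample falls on days 155-182, and a stray sample fills Week 36 only if none lies closer to day 252. A patient who attended Week 24 and stopped on day 195 keeps the Week 24 value. The documents do not show how often either case arises.

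No document requires halfway splits. The table does follow them, to within a day, at every other boundary between post-baseline visits, and it states durations at Weeks 8 and 36 that fit them. The reply therefore limits the size of the point without removing it.

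**Conclusion.** The point holds in limited form. Three durations are wrong as printed, and no counting convention that fits the other 19 rows rescues them. Two boundaries put 9 and 27 days (10 and 28 in SAP study days) into the farther visit. The day counts assume that nearness to the mid-point is the intended principle, as the selection rule suggests. The documents do not show whether the starts or the durations are the slip.

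The consequence is confined to late, unscheduled or discontinuation samples with no closer sample, in by-visit laboratory summaries: chiefly GH and IGF-I at Week 24 and the Week 8 and Week 36 rows. The primary endpoint, UFC, worst-value shift tables, and Weeks 12 and 48 are not materially affected. The number of records involved is unknown.

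Two further inferences go too far. The day-0 baseline row, and the screening mid-point of 0 outside its own window of −21 to −1, do not corrupt baseline: SAP 4.3 defines it as the last value before drug start. The table's end at day 1134 does not show that data will be lost. A patient on treatment on 13 June 2012, the date of the SAP version that incorporated amendment 3, and still treated on 31 December 2015 would have at least 1296 days, 162 past the last window. But treatment stops at approval and reimbursement if that comes first, and no document shows anyone followed so long.

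**What to change.** Move the two boundaries to about halfway between mid-points:

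- Week 4: days 26-42 (42 − 26 + 1 = 17 days)
- Week 8: days 43-70 (28 days, as already stated)
- Week 24: days 155-210 (210 − 155 + 1 = 56 days)
- Week 36: days 211-294 (84 days, as already stated)

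Correct the Duration column to match, including Weeks 4 and 24 and Week 1 (11 days if it stays at days 1-11). If the present wide windows are intended, say so, give a reason, and state 11, 38 and 112.

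As minor tidying, put the table on the SAP 4.2 day count (mid-points 8, 15, 22, 29, 57 and so on, with no day-0 row), and continue the 84-day rows past day 1134 if any patient is followed that long.

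The cost is one SAP table and one programming specification, with no new data. The change reduces early-stopper samples in later rows but does not eliminate them: a completion sample on day 215 would still enter Week 36, because unscheduled and completion samples are used. If that matters for interpretation, a footnote giving the number of such samples in each row would show it.
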